#### **Phase I Dose Finding Component:**

The Phase I component uses a continual reassessment method (CRM) to determine the maximum tolerated dose (MTD) of GTB-3550 TriKE. Up to 7 doses levels will be tested. The goal of the CRM is to identify the dose level which most closely corresponds to the targeted dose limiting toxicity (DLT) rate of 20%. Patients are enrolled in cohorts of 2 beginning at Dose Level 1. A minimum of 1 week must separate each patient. Both patients within a cohort must reach Day 28 (end of the DLT assessment period) prior to enrollment of a subsequent cohort. The study statistician assigns each new cohort of 2 patients to the most appropriate dose level based on updated toxicity probabilities. As enrollment proceeds, each cohort is assigned to an increased, decreased or equivalent dose level based on prior data in the trial until the study sample reaches 30. At this time, the last dose is declared the MTD and becomes the GTB-3550 TriKE dose for the extended component.

#### **Phase II Extended Component:**

The primary goal of the extended component is to study the potential efficacy of GTB-3550 TriKE in this patient population. Efficacy is measured using rates of complete and partial remission. A Simon's MiniMax two-stage design is used in this phase. Stage 1 will enroll 13 patients, including all patients treated at the MTD defined during the dose finding component. If 3 or more of these 13 patients experience a clinical response by Day 42, the trial moves to Stage 2 and enrolls an additional 17 patients. If at least 10 of the 30 patients have a disease response, GTB-3550 TriKE will be considered for further investigation. There is no staggering of enrollment for this cohort.

Primary Objectives:	
Phase I Dose Finding: To identify the maximum tolerated dose (MTD) of GTB-3550 TriKE defined as the dose level that most closely corresponds to a dose limiting toxicity rate (DLT) of 20%.
 
Phase II Extension: To determine preliminary efficacy as measured by the rates of “best” clinical response by Day 42 day after the start of the 1st infusion. For AML clinical response includes complete remission with or without hematologic or platelet recovery (CR, CRI or CRp) or partial response. For MDS clinical response includes complete remission, marrow CR (with incomplete peripheral blood count normalization), partial response or hematologic improvement (HI). For advanced systemic mastocytosis response is considered a decrease in mast cell burden in bone marrow or serum tryptase level by at least 30%.

Secondary Objectives:	

• To evaluate the safety of GTB-3550 TriKE when administered on this schedule

• To estimate overall survival (OS) at 6 months

Correlative Objectives:	

• To monitor the number, phenotype, activation status and function of NK cells, T cells, T regulatory cells and MDSCs pre- and post-therapy ( [REDACTED] [REDACTED] )

• To evaluate the pharmacokinetics and dynamics of the TriKE reagent

• To monitor for the development of human anti-TriKE antibodies

• To monitor the occurrence of antigen negative escape variants ( [REDACTED] ) in patients without response

Eligible Diseases:	
Diagnosis of one of the following CD33-expressing myeloid malignancies with greater than or equal to 50% CD33+ target cells with no good standard of care treatment options including:
 
High Risk Myelodysplastic Syndromes (MDS) progressive on two or more prior regimens and requiring treatment that meets at least one of the following:
 

• IPSS-R High or Very High Risk

• WHO Classification: RAEB-1 or RAEB-2

• Poor and very poor risk cytogenetic abnormality as defined by the IPSS-R cytogenetic classifications

• WHO Based Prognostic Scoring System (WPSS): High or Very High Risk

 
Therapy related MDS and not a candidate for induction chemotherapy or had an inadequate treatment response after induction chemotherapy
 
Acute Myelogenous Leukemia (AML) meeting at least one of the following:
 

• Refractory AML defined as failure to achieve remission after at least 3 induction attempts

◦ Elderly AML not fit for induction therapy can be enrolled after 2 failed inductions

• Relapsed AML meeting one of the following:

• Not a candidate for hematopoietic stem cell transplant (HSCT), at least one re-induction attempt required

• Prior HSCT relapse beyond 3 months may be included only if off immunosuppression for a minimum of 4 weeks and do not have GVHD

 
Advanced systemic mastocytosis (defined as mast cell leukemia, aggressive systemic mastocytosis, and systemic mastocytosis associated with hematologic neoplasm) may enroll without any prior treatment, given there is no standard established therapy.

**Key Inclusion Criteria:**

- Age  $\geq$  18 years of age, Karnofsky performance status  $\geq$  70%
- Adequate renal, hepatic, cardiac and lung function
- Absolute lymphocyte count (ALC)  $\geq$  200 cells/mm^3 OR absolute circulating CD56+/CD3- NK cell count  $>25$  cells/ $\mu$ L within the 14 days prior to start of therapy

[figure not shown]
**Enrollment:** Dose Finding Component: 30 patients enrolled in cohorts of 2 testing up to 7 GTB-3550 TriKE dose levels

Extended Component:

Stage 1: enroll 13 patients at the MTD (including any from the dose finding component treated at the MTD) – If 3 or more of these 13 patients experience a clinical response by Day 42, the trial will move to Stage 2

Stage 2: enroll 17 additional patients at the MTD established during the dose finding component

If the Phase I component enrolls more than 13 patients at the MTD, the futility rule for the two stage design will be adjusted with the given number of patients enrolled at the MTD.

**Each block consists of 4 consecutive 24 hour continuous infusion (CI) of GTB-3550 TriKE at the patient's assigned CI dose with a 72 hour rest after Block #1 and #2.**

**Dose Finding Phase I Component:**

Each patient receives GTB-3550 TriKE at the assigned CI dose for 3 sets (infusion block #1, #2, and #3) of 4 consecutive 24 hours infusions separated by a 72 hour rest.

Dose Level	GTB-3550 TriKE Dose daily continuous infusion (CI) dose ( $\mu\text{g/kg/day}$ )
1	5
2	10
3	25
4	50
5	100
6	150
7	200

The phase I component uses a continual reassessment method (CRM). Patients are enrolled in cohorts of 2 beginning at Dose Level 1. A minimum of 1 week must separate each patient. Both patients within each cohort must reach Day 28 (end of the DLT assessment period) prior to enrollment of a subsequent cohort. The study statistician assigns each new cohort of 2 patients to the most appropriate dose level based on updated toxicity probabilities. As enrollment proceeds, each cohort will be assigned to an increased, decreased or equivalent dose level based on prior data in the trial. Enrollment continues until the study sample reaches evaluable 30 patients. At that time the maximum tolerated dose (MTD) for the Phase II component will be identified.

**Dose Limiting Toxicity (DLT)** is defined as any related treatment emergent toxicity within 28 days (as assessed on Day 29) of the first dose of TriKE with the exception of those that are clearly and incontrovertibly due to extraneous causes for the following criteria based on CTCAE v5:

- Any Grade 4 or 5 non-hematologic events
- Grade 3 non-hematologic adverse events lasting more than 72 hours, except the following:
  - Non-sustained (< 7 days) Grade 3 liver function tests (ALT/AST, alkaline phosphatase, total or direct bilirubin) abnormalities in the absence of clinical signs of hepatic dysfunction (lethargy, confusion, anorexia, pruritus or tremors).
  - Non-sustained Grade 3 QTc prolongation (< 72 hours) in the absence of cardiac arrhythmia
  - Grade 3 electrolyte disturbances that resolve, with or without intervention, to < Grade 2 levels within 72 hours
  - Grade 3 fatigue
  - Grade 3 anorexia
  - Grade 3 fever
  - Grade 3 infection

- Hematologic Toxicity - Given that AML and MDS inherently leads to low neutrophils and platelets, standard grading cannot be used as many of these patients technically meet criteria for “grade 4” neutropenia or thrombocytopenia at baseline. Thus, the hematologic DLTs are listed below:
  - AML:
    - Grade 4 neutrophil count (<500/ $\mu$ L) lasting  $\geq$  29 days from start of cycle in absence of evidence of active leukemia
    - Grade 4 platelet count (<25,000/ $\mu$ L) lasting  $\geq$  29 days from start of cycle in the absence of active leukemia
    - Any clinically significant bleeding that is not controllable with transfusion support
  - MDS/mast cell diseases:
    - Grade 4 neutrophil count (<500/ $\mu$ L) lasting  $\geq$  29 days from start of cycle in absence of evidence of active MDS/mast cell disease
    - Grade 4 platelet count (<25,000/ $\mu$ L) lasting  $\geq$  29 days from start of cycle in the absence of active MDS/Mast cell disease
    - Any clinically significant bleeding that is not controllable with transfusion support
    - Grade 4 anemia, unexplained by the underlying disease
- Grade 3 infusion related, treatment related reaction including cytokine release syndrome which does not resolve within 72 hours despite best medical management (refer to [Section 10](#) for modified CRS grading)
- Grade 3 or 4 Tumor Lysis Syndrome that does not resolve within 7 days with or without intervention
- Inability to complete at least one block of three 24 hour infusions due to any treatment emergent, treatment related toxicity

**Maximum Tolerated Dose (MTD)** is defined as the dose level that most closely corresponds to the target DLT rate of 20%.

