## 12 Statistical Considerations

### 12.1 Study Design and Endpoints

This is a multisite Phase I/II study of GTB-3550 trispecific killer cell engager (TriKE) for the treatment of high risk MDS and relapsed AML. Once the MTD is identified, the objective will be to confirm safety and obtain preliminary estimates of efficacy as measured by the objective response, the **primary trial endpoint** as assessed between Day 21 and Day 42. For AML clinical response includes complete remission with or without hematologic or platelet recovery (CR, CRi or CRp) or partial response. For MDS clinical response includes complete remission, marrow CR (with incomplete peripheral blood count normalization), partial response or hematologic improvement (HI). For advanced systemic mastocytosis response is considered a decrease in mast cell burden in bone marrow or serum tryptase level by at least 30%.

All patients completing Block #1 will be evaluable for DLTs and toxicities. Patients who discontinue therapy prior to completion of both Block #1 and Block #2 will be replaced. Patients completing Block #1 and Block #2, but come off treatment for disease progression, will still be evaluable for efficacy and will not be replaced. If needed a subgroup of patients receiving all 3 blocks will also be evaluated for response as a secondary population. We expect that the number of patients coming off therapy after only completing block #1 will be minimal.

**Secondary trial endpoints** will include toxicity through Day 29 and overall survival (OS) at 6 months from 1st dose of study drug.

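### A related fatal hematologic event of an unlisted type after Block 1 is on no DLT line, so the CRM would score it as no DLT

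*Combined protocol and SAP*

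**What the plan says.** The DLT definition appears in the Study Schema, Section 7.2.1 and Section 10.3. The window is "any related treatment emergent toxicity within 28 days (as assessed on Day 29) of the first dose of TriKE" (schema wording).

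- **General severity line:** "Any Grade 4 or 5 non-hematologic events".
- **Hematologic toxicity:** standard grading is set aside because neutrophils and platelets are often already low at baseline. The text then says "Thus, the hematologic DLTs are listed below".
- **Items on that list:** Grade 4 neutrophils or platelets lasting at least "29 days from start of cycle in absence of evidence of active leukemia" (with a matching line for MDS/mast cell disease); "Any clinically significant bleeding that is not controllable with transfusion support"; and, under MDS/mast cell disease only, "Grade 4 anemia, unexplained by the underlying disease".
- **Fallback for any toxicity:** "Inability to complete at least one block of three 24 hour infusions due to any treatment emergent, treatment related toxicity".

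Section 12.1 says "All patients completing Block #1 will be evaluable for DLTs and toxicities". It also says that patients who stop therapy before completing both Block 1 and Block 2 are replaced. Section 10.5 makes deaths SAEs. The treatment-related mortality rule in Sections 10.4 and 12.4 applies to the Phase II component only.

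**The concern.** The reason given for treating hematologic toxicity separately is low baseline neutrophils and platelets. That explains why count grades are unusable. It does not explain why a related hematologic death should fall outside the definition. If a death meets no line, the CRM reads that patient as having tolerated the dose, with cohorts of only two patients behind each assignment. The only other Phase I stop, in Section 12.4, uses the posterior for the lowest dose and so depends on the same DLT scores.

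There is also an asymmetry between diseases. A related, unexplained Grade 4 anemia is a DLT in MDS or mast cell disease but is not listed for AML, although one dose-toxicity curve is fitted to all patients. To that extent the estimated DLT rate at a dose depends on the disease mix as well as the dose.

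**Working it through.** **Step 1. Trace the clearest case: related fatal anemia in an AML patient, after Block 1 and by Day 28.**

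| DLT item | Met? |
|---|---|
| Grade 4-5 line | No: limited to non-hematologic events |
| Grade 4 neutrophils or platelets for at least 29 days | No: a patient who dies by Day 28 cannot reach 29 days |
| Uncontrollable bleeding | No, unless bleeding is the cause |
| Unexplained Grade 4 anemia | No: not listed for AML |
| Infusion reaction/CRS, tumor lysis | No |
| Unable to complete one block | No: Block 1 is complete. This item speaks of three infusions and a block elsewhere has four, but it is exhausted on either count |

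**Step 2. When the gap is open.** By Section 10.2, Blocks 1 and 2 end on Days 5 and 12. From Day 12 to Day 28 the patient is DLT-evaluable with no DLT. From Day 5 to Day 12, Section 12.1 both calls the patient DLT-evaluable and says the patient is replaced. On neither reading is the death a DLT. These days assume no block delay.

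**Step 3. Effect on the CRM.** Inputs from Sections 12.1 and 12.4:

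- Model: p_i = d_i^exp(α), with α ~ N(0, 0.5).
- Target: 20%. Cohorts of 2. No skipping on escalation.
- Safety stop: P(Level 1 DLT rate > 20%) above 90%.
- Skeleton: 3, 5, 7, 10, 14, 17 and 20%. Section 12.1 still lists six values and gives 17% as the expected true probability at 150 µg/kg. Using it as the Level 6 skeleton value is an assumption.

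The posterior of α was computed on a grid, and the next dose is the level whose estimated DLT probability is closest to 20%. The plan does not say whether the estimate is a posterior mean or a plug-in at the mean of α, so both were run. The plan states no figure for this point that could be reproduced first.

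Next level assigned, with 0/2 at every lower level:

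| Current level | 0/2 | 1/2 | 2/2 |
|---|---|---|---|
| 1 | 2 | 1 | 1 |
| 2 | 3 | 2 (plug-in 3) | 1 |
| 3 | 4 | 4 | 1 (plug-in 2) |
| 4 | 5 | 5 | 3 |
| 5 | 6 | 6 | 4 |
| 6 | 7 | 7 | 5 |

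- **One rescored event and no other DLT (0/2 to 1/2):** the assignment changes at Level 1 and, by posterior mean only, at Level 2. At Levels 3 to 6 it does not change. At Level 1, P(DLT rate > 20%) goes from 0.07 to 0.46, still under the 0.90 stop. At Level 4 the estimated rate goes from 0.06 to 0.16 without changing the next dose.
- **One rescored event and another DLT in the same cohort (1/2 to 2/2):** Level 4 goes from assigning 5 to 3, Level 5 from 6 to 4, and Level 6 from 7 to 5, under both estimates.
- **An earlier DLT (1/2 at Level 5, 0/2 below) and one event at Level 6:** scored 0/2, the posterior means for Levels 5, 6 and 7 are 0.139, 0.165 and 0.192, so Level 7 is assigned. Scored 1/2, they are 0.207, 0.239 and 0.270, so Level 5 is assigned. The plug-in agrees.

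**Step 4. Contrast with Phase II.** The mortality rule in Sections 10.4 and 12.4 counts non-relapse, non-infectious treatment-related deaths within 60 days and has no hematologic exclusion. The same death would count there, but not in the phase that selects the dose.

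**The case against.** The narrowing of the hematologic items was deliberate. The revision history records that the parameters were changed because of baseline disease, and that febrile neutropenia was taken out of the MDS/mast cell definition. Much is still caught: uncontrollable bleeding is listed for all diseases, only Grade 3 infection is exempt, and any related toxicity that prevents completion of one block counts. This stands, and it makes the gap narrow. It does not close it, because the stated rationale concerns neutrophil and platelet counts and not deaths.

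A reader might infer three stronger things that the documents do not support:

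- **That fatal febrile neutropenia, hemolysis or coagulopathy is certainly missed.** The protocol does not define which events are hematologic. If these are classed as non-hematologic, the Grade 4-5 line captures them.
- **That every such death from Day 5 onward enters the CRM as no DLT.** Before Block 2 is complete, the replacement rule may take the patient out of the data. It is also unclear how a patient who has died satisfies the requirement that both cohort members reach Day 28.
- **That one unscored death generally pushes the dose up.** With no other DLT, it leaves the next assignment unchanged at Levels 3 to 6.

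It is also fair to object that a DLT ends treatment for any patient (Sections 7.1.5 and 7.5). Rewriting the Grade 4 items would therefore alter clinical management. That is why the change below is confined to the scoring of Grade 5 events.

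**Conclusion.** The concern holds in a limited form. As written, a related Grade 5 hematologic event of an unlisted type, after Block 1 and by Day 28, is on no DLT line and no Phase I rule catches it. Anemia in AML is the clearest example. Clean scoring as no DLT is certain only once Block 2 is complete; before that the patient's place in the data is contradictory.

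The effect is decisive at Level 1, and at Level 2 under the posterior mean. It is also decisive in the cases shown where another DLT has occurred, where the assigned level differs by two. It is nil for a single event with no other DLT at Levels 3 to 6. These results rest on 17% as the Level 6 skeleton value and on choosing the level closest to 20%. They concern level numbers only; the smaller dose increments that Section 7.2.1 triggers after a DLT were not modeled.

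**What to change.** 1. In the schema, Section 7.2.1 and Section 10.3, state that for CRM scoring a related Grade 5 event within 28 days counts as a DLT, whether hematologic or not.
2. In Section 12.1, state that such a patient stays in the CRM data and is not replaced, and reconcile this with the evaluability and replacement sentences there. State how the Day 28 requirement for opening the next cohort applies after a death.
3. Reconcile the Grade 4 anemia item, listed for MDS/mast cell disease but not AML, with the single curve fitted to all diseases. Reconcile the breadth of the hematologic carve-out with its neutrophil and platelet rationale. How these are resolved, and any effect on stopping treatment, is for the sponsor; no rule is proposed here.
4. Say whether a Grade 5 event scored this way also triggers the smaller-increment rule in Section 7.2.1.

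Item 1 costs one line in three places and an update to the DLT form; items 2 to 4 need a few further sentences. No procedures are added. The downside is that a few more events may be scored as DLTs.

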**Additional Dose Escalation Parameters (Phase I Only):**

In addition to monitoring for dose limiting toxicity, patients enrolled in the Phase I component will be monitored for signs of immune activation using treatment related tachycardia and fever as clinical markers of transient bioactivity resulting from endogenous cytokine release. If detected in a single patient, subsequent dose levels will increase by 50% instead of the planned doubling (100% increase).

**Extended Phase II Component:**

Patients will receive three consecutive blocks of four 24 hour continuous infusions of GTB-3550 TriKE at the Phase I MTD separated by a 72 hour rest. There is no staggering of enrollment for this component.

**Stage 1:** Enroll a total of 13 patients (including all treated at the MTD in Phase I). If 3 or more of these patients have clinical response by Day 42 the trial will continue to Stage 2. If the Phase I component enrolls more than 13 patients at the MTD, the futility rule for the two-stage design will be adjusted with the given number of patients enrolled at the MTD.

**Stage 2:** Enroll an additional 17 patients. If 10 of 30 patients have a clinical response by Day 42, GTB-3550 TriKE will be considered promising for further investigation.

**Monitoring for Safety (Phase II Extended):**

- Grade 4-5 non-hematologic, non-relapse, non-infectious toxicity (except fever) by 42 days after the start of the first GTB-3550 TriKE treatment block
- Non-relapse, non-infectious treatment related mortality within 60 days of the 1st dose of GTB-3550 TriKE

## 1 Objectives

### 1.1 Primary Objective

Phase I Dose Finding: To identify the maximum tolerated dose (MTD) of GTB-3550 TriKE defined as the dose level that most closely corresponds to a dose limiting toxicity rate (DLT) of 20%.

Phase II Extension: To determine preliminary efficacy as measured by the rates of “best” clinical response by Day 42 after the start of the 1st infusion.

For AML clinical response includes complete remission with or without hematologic or platelet recovery (CR, CRi or CRp) or partial response. For MDS clinical response includes complete remission, marrow CR (with incomplete peripheral blood count normalization), partial response or hematologic improvement (HI). For advanced systemic mastocytosis response is considered a decrease in mast cell burden in bone marrow or serum tryptase level by at least 30%.

### 1.2 Secondary Objectives

- To evaluate the safety of GTB-3550 TriKE when administered on this schedule
- To estimate overall survival (OS) at 6 months

### 1.3 Correlative (Research) Objectives

- [REDACTED]
- To evaluate the pharmacokinetics and dynamics of the TriKE reagent
- [REDACTED]
- To monitor the occurrence of antigen negative escape variants (CD33- blasts) in patients without response

[figure not shown]
## 2 Background

Acute myeloid leukemia (AML) is a heterogeneous hematologic stem cell malignancy in adults with incidence rate of 3–5% per 100,000 populations. The median age at the time of diagnosis is 65–69 years. AML is an aggressive disease and is fatal without anti-leukemic treatment. Myelodysplastic syndromes (MDS) are a heterogeneous group of myeloid neoplasms characterized by dysplastic features of erythroid/myeloid/megakaryocytic lineages, progressive bone marrow failure, a varying percentage of blast cells, and enhanced risk to evolve into acute myeloid leukemia. The incidence of MDS is rising especially in states like Minnesota for unknown reasons. There are few established treatments for MDS so a drug that could be successfully employed

[figure not shown]
to treat AML and MDS would be extremely valuable. The expression of cell surface markers in MDS is complicated by its heterogeneous nature and has only been recently brought to light with the work of the First Workshop on Standardization of Flow Cytometry in MDS convened in Amsterdam bringing together experts from Europe, Japan, and the USA. The workshop found that a majority of MDS cases showed an abnormally high expression of HLA-DR, CD64, and CD33. We believe that CD33 is a validated target in AML and can also target MDS cells to promote a novel targeted immunotherapy approach for these diseases.

Targeted cancer immunotherapies are currently a subject of great clinical interest and potential. While a great deal of interest has recently been placed upon generation of chimeric antigen receptor (CAR) expressing T cells from monoclonal antibodies shown to target human malignancies, and more even more recently upon generation of CAR-expressing natural killer (NK) cells, these approaches require a personalized approach that is expensive, time consuming, and difficult to apply on a large scale. There is a clear need for targeted off-the-shelf therapies that augment the current monoclonal antibody approach. To accomplish this goal, we focus on generation of tri-specific killer engagers (TriKEs) meant to target NK cells to the tumor synapse and induce their activation at that site. Unlike full-length tri-specific antibodies, [REDACTED]

In human NK cells,

The efficacy of therapeutic mAbs *in vivo*, in contrast to their high ADCC efficacy *in vitro*, is further attenuated by the presence of physiologic serum IgG levels in plasma. In the *in vivo* setting, ADCC potency is diminished by saturation of CD16 receptors, thus competing for binding with the therapeutic mAb . Such competition for binding of the therapeutic Fc portion of antibodies requires high serum levels of the mAb to be sustained over several months of treatment in order to achieve *in vivo* efficacy .

These attributes make them an ideal pharmaceutical platform for potentiated NK cell-based immunotherapies.

